6.3.4 Safety outcomes

The AESI evaluated in this study include the following categories:

- serious infections
- opportunistic infections including PML
- hepatitis B reactivations
- serious infusion related reactions
- malignancies

Diagnosis codes to identify safety outcomes of interest are listed in [Table 12](#) in Annex 3. Real-world study operational definitions for serious infection, opportunistic infections and hepatitis B reactivations will be defined as local ICD-9/ICD-10 diagnoses codes in

inpatient hospitalizations during the follow-up. Real-world study operational definitions for serious infusion related reactions will be defined as local ICD-9/ICD-10 diagnoses coded in inpatient hospitalizations, outpatient visits or as documented adverse events depending on available data. Safety outcomes will be retrieved during the follow-up with their date of occurrence.

[figure not shown]

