The overall study period will be from the date of inebilizumab market availability (the earliest Q3 2022) until December 2027 the latest. Index date will be defined as the date of inebilizumab initiation (first administration/prescription/dispensation depending on data available in selected data source). Patients will be followed for 12 months after the index date or censored if end of the study period or loss of follow-up (death, disenrollment/de-registering) whichever occurs first.

Population: The study population will be identified in national healthcare administrative databases, claim databases and disease-specific registries and will include adult (18 years old or more at the index date) female and male patients diagnosed with NMOSD and initiating inebilizumab during the study period.

Variables: Exposure to inebilizumab will be defined by the existence of records of administration/prescription/dispensation with the Anatomic Therapeutic Chemical (ATC) code L04AA47/L04AG10 from 2024 onwards). Baseline characterization will consider demographics, comorbidities, NMOSD-related clinical characteristics (disease duration, NMOSD core symptoms and NMOSD-associated conditions, presence of autoantibodies against aquaporin-4 and myelin-oligodendrocyte glycoprotein, history of relapses), previous immunosuppressive therapies, and inebilizumab initiation characteristics (setting of healthcare and specialty of prescribers, and treatment indication).

Inebilizumab treatment patterns during a 12-month follow-up will be characterized in terms of duration, dosing, frequency of drug discontinuation, switching, and use of add-on therapies considering the dates of inebilizumab administration/prescription/dispensation and the respective estimated end dates of the drug exposure period.

AESI grouped in 5 categories (serious infections, opportunistic infections, hepatitis B reactivations, serious infusion related reactions, and malignancies) will be identified using the International Classification of Diseases, 9th or 10th revision codes. Serious infection, opportunistic infections, hepatitis B reactivations and serious infusion related reactions will be captured if leading to inpatient hospitalization or outpatient visit during the follow-up.

Data Sources: This study involves secondary use of data from data sources across 5 European countries:

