6.4.3 Spain

The Information System for Research in Primary Care (*Sistema d'Informació per al Desenvolupament de la Investigació en Atenció Primària* [SIDIAP]), IDIAP Jordi Gol (Spain) is a primary care records database that covers approximately 7 million people, equivalent to an 80% of the population of Catalonia, North-East Spain. SIDIAP is collected from EHR records of patients receiving primary care delivered through Primary Care Teams (PCT), consisting of general practitioners, nurses and non-clinical staff. The Catalan Health Institute manages 286 out of 370 such PCT with a coverage of 5.6 million patients, out of 7.8 million people in the Catalan population (74%). The database started to collect data in 2006. The mean follow-up is 10 years. The observation period for a patient can be the start of the database (2006), or when a person is assigned to a Catalan Health Institute primary care center. Date of exit can be when a person is transferred-out to a primary care center that does not pertain to the Catalan Health Institute, or date of death, or date of end of follow-up in the database. Drug information is available from prescriptions and from dispensing records in pharmacies. Studies using SIDIAP data require previous approval by both a Scientific and an Ethics Committee (20). For a subset of patients included in the SIDIAP database, linkage to hospital data is available as obtained from the Catalan Institute of Health hospitals (21) and will be further explored in the feasibility assessment. Healthcare is universal and taxpayer funded in the region, and primary care physicians are gatekeepers for all care and responsible for repeat prescriptions. SIDIAP-Hospitalization Linked Data has contributed to studies involving patients with MS (21).

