6.4.4 Italy

The Italian Multiple Sclerosis & Related Disorders Register (*Registro Italiano Sclerosi Multipla e Patologie Correlate* [RISM]) was officially established in 2015. As of February 2023, the register was actively covering 133 MS centers, corresponding to a total of 80,353 patients, of which 273 are diagnosed with NMOSD. Since July 2022, the

register comprises a module for the collection of information on NMOSD, and has projects dedicated to NMOSD patients (22). Nonetheless, data on NMOSD patients were collected previous to 2022, without a specific module implemented. The data are collected from participating centers through a web-based system developed for the study, available at the IMS&RD website. Data are collected from accrual to exit of database, which may occur at date of death, when patient moves to a center outside of the covered network or withdraws their consent to participate. The data are centrally monitored to ensure quality of data, completeness, accuracy, and consistence (23). Requests to access the data are evaluated by the Scientific Committee, composed by clinicians, methodologists, representatives of MS centers, and of the Italian Neurological Society (23).

To ensure the collection of sufficient data for the clinical characterization of the single patient mandatory variables collected by the register include patient identification, demographics, vital status, disease onset date, diagnosis date, relapses, treatments and severe adverse events. This minimum dataset may be completed with an extension to optional information on family history, comorbidities, laboratory tests and MRI. Furthermore, the register has data on patient's unique personal identifier, to avoid inclusion of the same patient by more than 1 center. Diagnosis information is available and captured with ICD-9-CM coding system.

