		787.7	R19.5	
		787.99		
	Pyrexia	780.60	R50 R50.2 R50.8 R50.9	
		Chills	780.64	R68.8
		Fatigue	780.79	R68.8
		Chest discomfort	786.5	R07
	786.50		R07.3	
786.59	R07.4			
Pain	Pain, not elsewhere classified	R52 R52.0 R52.9		
	Acute pain			
Back pain	724.5	M54.9		
Myalgia	729.1	M79.1		

Classification	Conditions	Diagnosis ICD-9 -CM Codes*	Diagnosis ICD-10-CM Codes*
	Headache	784.0	R51
	Dysgeusia	781.1	R43.2
	Dizziness	780.4	R42
	Dyspnea	786.05	R06.0
	Oropharyngeal pain	784.1	R06.0
	Cough	786.2	R05
	Rash	782.1	R21
	Urticaria/ Erythema	708 708.9 782.9	R23 R23.8 L50 L50.9
	Pruritus	782.1 698	R21
	Rash pruritic	782.1	R21
	Flashing	782.62	R23.2
Infusion related reactions	Generalized skin eruption due to drugs and medicaments	693.0	L27.0
	Localized skin eruption due to drugs and medicaments	-	L27.1
	Complications following infusion, transfusion and therapeutic injections	999.34 999.39	T80
	Other complications following infusion, transfusion and therapeutic injection	999.88 999.89	T80.8
	Unspecified complication following infusion, transfusion and therapeutic injection	999.80	T80.9
	Anaphylactic shock due to adverse effect of correct drug or medicament properly administered	999.4	T88.6
	Unspecified adverse effect of drug or medicament	995.20 995.29	T88.7
	Anaphylactic shock, unspecified	995.0	T78.2
	Angioneurotic oedema	995.1	T78.3

Classification	Conditions	Diagnosis ICD-9 -CM Codes*	Diagnosis ICD-10-CM Codes*
	Allergy, unspecified	995.3	T78.4
	Shock, not elsewhere classified		R57
	Other shock	785.59	R57.8
	Shock, unspecified	785.50	R57.9
Malignancies		140-209	C00-C96

Abbreviations: ICD-9/ICD-10: 9th/10th Revision of International Classification of Diseases, CM, Clinical Modification.

*ICD-X-CM codes will be translated into local ICD-X codes and provided in SAP

#captured if leading to infection-related in-patient hospitalization during the follow-up

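### The care setting for infection AESI is defined two ways, and the inpatient-only version does not fit the Italian registry or unlinked SIDIAP patients, who stay in the denominator

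*Protocol*

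**What the plan says.** Three places in the protocol set the care setting for serious infections, opportunistic infections and hepatitis B reactivations.

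- Abstract, Variables: "Serious infection, opportunistic infections, hepatitis B reactivations and serious infusion related reactions will be captured if leading to inpatient hospitalization or outpatient visit" during follow-up.
- Section 6.3.4: "definitions for serious infection, opportunistic infections and hepatitis B reactivations will be defined as local ICD-9/ICD-10 diagnoses codes in" "inpatient hospitalizations during the follow-up".
- Annex 3, Table 12 footnote, attached to the same three categories: "captured if leading to infection-related in-patient hospitalization during the follow-up".

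For serious infusion related reactions, 6.3.4 is wider: "diagnoses coded in inpatient hospitalizations, outpatient visits or as documented adverse events depending on available data".

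Two source descriptions bear on whether the inpatient rule can be applied. In section 6.4.4, the mandatory content of the Italian registry (RISM) ends with "diagnosis date, relapses, treatments and severe adverse events". Comorbidities, laboratory tests and MRI are optional, coding is ICD-9-CM, and hospital stays or discharge diagnoses are not listed. Section 6.4.3 describes SIDIAP as a primary care database and adds: "For a subset of patients included in the SIDIAP database, linkage to hospital data is available". The size of that subset is not given.

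Section 6.7.2.3 divides incident AESI reports by all patients. It does not limit the denominator to patients whose inpatient events can be seen.

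**The concern.** An infection coded at an outpatient visit counts under the abstract and does not count under 6.3.4 and Table 12. That affects three of the five AESI categories in a safety study, and the category that includes PML is one of them.

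The inpatient-only rule raises a second problem. A serious infection recorded in RISM as a severe adverse event has no stated route into the numerator, because 6.3.4 gives the adverse-event route to infusion reactions alone. A SIDIAP patient without hospital linkage has no described source of inpatient codes. Both kinds of patient still contribute to the denominator of the cumulative incidence, and their follow-up still counts as time at risk for the incidence rate. A low Italian or Spanish figure could then be read as low risk when it reflects the capture rule.

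**Working it through.** **1. The contradiction.** This needs no arithmetic. The abstract accepts inpatient or outpatient contacts. Section 6.3.4 and Table 12 accept inpatient only. The operational section and the code table agree with each other, so the abstract is the outlier.

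**2. Route into the numerator, taking 6.3.4 literally.**

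| Patients | Inpatient codes described? | Adverse-event route for infections? | In denominator? |
|---|---|---|---|
| RISM | Not listed | No (infusion reactions only) | Yes |
| SIDIAP, hospital-linked | Yes | Not needed | Yes |
| SIDIAP, unlinked | No | No | Yes, if identified as exposed |

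Under the abstract's rule, unlinked SIDIAP patients might contribute events, but the protocol does not say whether a primary care contact counts as an outpatient visit.

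**3. The plan's own precision figures.** Section 6.5 uses n = 1.96² × p(1 − p)/d².

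- p = 1%, d = 1%: n = 380.3 (Table 3: 380).
- p = 4%, d = 2%: n = 368.8 (Table 3: 369).
- At n = 400 the half-widths are 0.98 and 1.92 points.

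Table 3 is correct. It presumes that events can be seen in every patient counted.

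**4. Illustration of dilution.** Assumptions: inebilizumab users are spread across sources as the NMOSD patients in Table 4, true risk is equal everywhere, and sources are simply summed.

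- Italian share s_IT: 208/576 = 36.1%; 1,756/4,870 = 36.1%.
- Spanish share s_ES: 29/576 = 5.0%; 246/4,870 = 5.1%.
- c = fraction of Italian events captured; u = fraction of Spanish patients unlinked. Neither is given, so both run from 0 to 1.

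Displayed risk = true risk × [1 − s_IT(1 − c) − s_ES·u]

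| c | u | Factor | True 4% shows as | True 1% shows as |
|---|---|---|---|---|
| 0 | 0 | 0.639 | 2.6% | 0.64% |
| 0 | 1 | 0.589 | 2.4% | 0.59% |
| 0.5 | 0 | 0.82 | 3.3% | 0.82% |
| 0.5 | 1 | 0.77 | 3.1% | 0.77% |
| 1 | 1 | 0.95 | 3.8% | 0.95% |
| 1 | 0 | 1.00 | 4.0% | 1.00% |

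In the two rows with c = 0, only 400 × 0.639 = 256 or 400 × 0.589 = 236 of 400 patients could yield an infection event. The half-widths would then be about 1.2 to 1.3 points at 1% and 2.4 to 2.5 points at 4%.

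**5. Sensitivity to the Italian share.** Table 4 applies prevalence to about 39.9 million adults, but section 6.4.4 reports 273 NMOSD patients in the registry in February 2023. Keeping the 2006-criteria counts for the other countries:

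- Lower counts: 273/(26 + 29 + 36 + 277 + 273) = 273/641 = 43%.
- Upper counts: 273/(220 + 246 + 308 + 2,340 + 273) = 273/3,387 = 8%.

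With no Italian capture and full Spanish linkage, a true 4% would show as 2.3% or 3.7%. On these totals Spain's share would be 29/641 = 4.5% or 246/3,387 = 7.3%, against about 5% on Table 4's own totals.

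**The case against.** The strongest reply has four parts.

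- **Italy is not blind to these events.** Severe adverse events are mandatory in RISM and diagnoses carry ICD-9-CM codes. The variable list is introduced as what the mandatory items include, so it may not be complete. Section 6.4 says that availability of safety outcomes was a criterion for choosing sources. This stands: a reader might infer that Italy would contribute no infection events, and the documents do not show that. What is missing is a rule that lets the recorded events count.
- **Unlinked SIDIAP patients may never enter the cohort.** The drug is given in secondary care (6.9), while SIDIAP drug data come from prescriptions and pharmacy dispensing (6.4.3). Patients without linkage may not be identified as exposed. This stands too, and the Spanish contribution could be close to nil.
- **No pooled estimate is fixed.** Section 6.7.1 analyses each source separately and allows a meta-analysis only if events per source suffice, a condition that a source with no events would fail. The 400-patient pooled cohort in 6.5 illustrates precision. So pooled dilution is conditional, and the direct harm is at source level.
- **Detail belongs in the SAP.** The protocol leaves outcome definitions, local codes and the incident-report algorithm to it. That covers detail, but the care setting is fixed in the protocol, in two incompatible ways. A SAP can follow only one of them.

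Section 6.9 does concede that safety outcomes may be underestimated and suggests that registries may reduce this. For infections, the wording of 6.3.4 closes that route.

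**Conclusion.** The contradiction between the abstract and section 6.3.4 with Table 12 is certain and rests on no assumption. The misfit of the inpatient-only rule with RISM, and with any unlinked SIDIAP patient who enters the cohort, follows from the protocol's own source descriptions and its unrestricted denominator. The consequence is infection estimates that are understated or not comparable for those sources, with dilution of a pooled figure only if sources are combined.

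The size is illustrative. A fall from 4% to about 2.6% needs all of the following: no Italian capture, Table 4 shares, equal risk and simple summing. Table 4 counts NMOSD patients, not inebilizumab users.

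The finding should not be extended to PHARMO or NOMADMUS, because the documents show no such defect there. Nor is it an error that malignancies carry no setting: all three places consistently leave them unrestricted. The point should be fixed, but it does not invalidate the study.

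**What to change.** 1. Correct the abstract so that the three infection categories carry the same inpatient rule as 6.3.4 and the Table 12 footnote.
2. In 6.3.4, allow registry-documented severe adverse events to count for these three categories where a source has no inpatient records, and label this as a source-specific definition wherever results appear.
3. In 6.7.2.3, restrict the numerator and denominator of the infection AESI analyses, including time at risk, to patients with the required ascertainment. In SIDIAP that means patients with hospital linkage.

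The cost is protocol wording and a linkage flag in SIDIAP. The Spanish denominator for infection AESI may become somewhat smaller. Definitions will differ by source: a severe adverse event in a registry is not the same endpoint as an inpatient code, so the difference must be shown and weighed before any pooling.

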6.4 Data Sources

The inclusion of a country/data source in the study was based on the evaluation of the following aspects:

- time of inebilizumab launch (focus on the initial countries to launch inebilizumab)
- availability of data required to meet the study objectives (i.e., exposure to inebilizumab and other disease modifying drugs, safety outcomes)
- data bases in which the number of exposed patients was relatively high
- data availability in the defined study period, after taking into account the lag time (time from data capture to data available in the system)

The evaluation of the last 3 aspects was carried out through a detailed qualitative feasibility assessment in 17 different data sources in 9 countries. Ultimately, 6 data sources from 5 European countries were included in the study (Figure 3 Data Sources Included).

Figure 3 Data Sources Included

6.4.1 France

The French National Health Data System (Système National des Données de Santé [SNDS])

SNDS is the largest and most comprehensive healthcare dataset available in Europe with a 10-year longitudinal follow-up for more than 65 million individuals (including 50 million adults), and is highly representative of the French residents, covering 99% of the total population (15). Individuals enter the data source once born within or immigrating to the specific geographical area, and exit the data source either at date of death, emigration, or ending their insurance.

SNDS contains anonymized administrative and healthcare claims data from the French national health care insurance system databases including main health care claims database, ie., French National health insurance information system (*Système national d'information interrégimes de l'Assurance maladie* [SNIIRAM]), hospital discharge summaries (*Programme de Médicalisation des Systèmes d'Information* [PMSI]), and national death registry (Centre d'épidémiologie sur les causes médicales de Décès) (16).

SNDS contains information on beneficiaries age, sex, region of residence, death date, complementary universal health coverage status, and all out-patient healthcare drugs including all reimbursed prescription drugs identified by their ATC code, the date of delivery, quantity, and brand name. Medical procedures performed on an out-patient basis or in a healthcare institution are identified by the common classification of medical procedures (*classification commune des actes médicaux*), laboratory procedures are identified by the clinical pathology test nomenclature (*nomenclature des actes de biologie médicale*), and paramedical or medical visits are identified by the general nomenclature of professional procedures (*nomenclature générale des actes professionnel*).

The French National Health Insurance Information System, SNIIRAM

SNIIRAM was created in 2003 and contains healthcare information generated through the reimbursement scheme of the French national health insurance. The French National Health Insurance Fund for Salaried Workers (*la Caisse nationale de l'assurance maladie des travailleurs salariés* [CNAMTS]) (the general scheme) covers approximately 87% of the population including employees in the industry, business, and service sectors; public service employees; and students. A range of additional insurance schemes, such as those dedicated for self-employed and agricultural workers and others, cover the remaining population.

SNIIRAM includes data on sociodemographic, diagnoses of chronic conditions, health care encounters such as physician or paramedical visits, medicines, medical devices, and lab tests (without results); outpatient medical expenses including dispensed medication, medical visits and procedures, date and duration of hospitalizations, inpatient diagnoses and procedures (15). However, some health care consumptions cannot be seen, such as consumptions not claimed for reimbursement, not reimbursable health services, and self-medication. Moreover, the only in-hospital prescriptions included are those of expensive drugs that are excluded of the hospital diagnosis-related groups (e.g., targeted cancer therapies and monoclonal antibodies) (16).

French Hospital Décharge Sommaires, PMSI

SNIIRAM claims database can be linked with the PMSI via unique individual identifiers. Data from PMSI includes medical summaries of all hospitalizations from all private or public hospitals across different types of care centers: acute care (short duration stays) at hospital, home hospitalizations stays, follow-up and rehabilitation care stays.

PMSI provides the date of stay, medical procedures performed during hospital stay, costly innovative drugs (*medicaments “listed en sus”*) or implantable devices received during the hospital stay, the primary diagnosis (main reason for admission), related diagnoses (specific to the disease context of the primary diagnosis), and diagnoses related to other comorbidities, all encoded according to the ICD-10. Information on occupational diseases and sick leaves is also available.

French MS Registry

French MS Registry (Observatoire Français de la Sclérose en Plaques [OFSEP]) was established in 2003; it is a national register actively covering data from 36 centers corresponding to 42 databases, of which 2 contain exclusively NMOSD patients. The data is collected from participating centers using the European Database for Multiple Sclerosis software. OFSEP covers approximately 50% of the total MS population in France and holds data for approximately 55,000 patients in total. Of these, 23,000 patients have records after June 2013, when a minimal data threshold was established. OFSEP contains information such as personal and sociodemographic information, clinical, paraclinical (e.g., MRI), and therapeutic data (disease-modifying treatments). Access to the data is made directly via an application to the database: the National Coordination Center and the Scientific Board of the database evaluate the applications and the Steering Committee makes the final decision (17).

French NMOSD Registry

Nested within the OFSEP is a French NMOSD registry recruiting patients with NMOSD presentations in France (*Neuro-Optico-Myélite Aiguë de Devic et des syndromes neurologiques apparentés* [NOMADMUS]). The cohort was initiated in 2010 and gathers clinical, biological and imaging data (18). The patients are regularly tested for anti-AQP4 and anti-MOG, and all cases are reviewed by an expert committee (19).

